Investigation of Pupillometry as Guide for Extubation Readiness in Anesthetized Children

NCT04947397

07/01/2024

Aims/Objectives

- 1/ Increase the safety of tracheal extubation in pediatric anesthesia.
- 2/ Define an objective, quantitative metric to guide extubation in anesthetized pediatric patients.
- 3/ Demonstrate a method to decrease anesthetic vapor requirements for extubation and thereby decrease the time interval that patients are subject to the risks of anesthetic vapor.
- 4/ Compare pupillometry method to a traditional extubation method.

Study Protocol

In pediatric patients undergoing general anesthesia for surgery, subjects will be randomized to two groups: Group 1/ Deep vapor extubation group, and Group 2/ Pupillometry group.

For subjects randomized to Group 1, the protocol is as follows:

At the conclusion of surgery and in preparation for tracheal extubation, spontaneous ventilation will be reinitiated and a deep plane of anesthesia will be established with anesthetic vapor set at 1.5 MAC (sevoflurane ~3.75%) for 8 minutes. This follows a traditional method for deep extubation. The subject will then be extubated. Immediately following extubation, 100% O₂ will be given via an anesthesia mask together with 5 cm H₂O CPAP and a gentle jaw thrust, which is the standard practice of the authors. Following standard practice, anesthetics and equipment necessary to manage any extubation issue will be prepared and immediately available.

Ventilation will be monitored in a standard manner, using chest wall movement, capnography, reservoir bag movement, condensation of anesthetic mask and auscultation. Oxygenation will be monitored by continuous pulse oximetry and skin color.

For subjects randomized to Group 2, the protocol is as follows:

- 1/ At the conclusion of surgery and in preparation for tracheal extubation, spontaneous ventilation will be reinitiated and a deep plane of anesthesia will be established with anesthetic vapor set at < 0.5 MAC together with titrated increments of propofol and fentanyl as appropriate at discretion of anesthesiologist.
- 2/ Pre-stimulus pupillometry: Measure pupil with portable infrared pupillometer. 2 measurements will be made to establish a stable baseline.
- 3/ Perform standardized laryngeal stimulus (deflate ETT cuff, withdraw ETT 1 cm, readvance ETT 1cm, reinflate ETT cuff).
- 4/ Post-stimulus pupillometry. Measure pupil size. 2 measurements will be made, the first within 30 seconds of laryngeal stimulus, the second within 30 seconds of the 1st measurement. PRD = Post-stimulus pupil size - pre-stimulus pupil size.
- 5/ Decision analysis. If PRD < or = 0.10 mm, extubate. If PRD > 0.10 mm, deepen patient with increments of propofol and/or fentanyl at anesthesiologist discretion, then repeat sequence of

pre-stimulus pupillometry, standardized laryngeal stimulus, post-stimulus pupillometry, decision analysis.

6/ If protocol iterates 3 times, the anesthesiologist will extubate when clinically appropriate irrespective of PRD.

7/ Immediately following extubation, 100% O₂ will be given via an anesthesia mask together with 5 cm H₂O CPAP and a gentle jaw thrust, which is the standard practice of the authors.

Following standard practice, anesthetics and equipment necessary to manage any extubation issue will be prepared and immediately available. Ventilation will be monitored in a standard manner, using chest wall movement, capnography, reservoir bag movement, condensation of anesthetic mask and auscultation. Oxygenation will be monitored by continuous pulse oximetry and skin color.

Statistical Analysis Plan

Calculation of descriptive statistics (mean, median, standard deviation) for parameters:

- Age
- Sevoflurane concentration
- Pupillometry

Estimation of differences between Groups on Outcome #1 with comparison by T test.

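### Does the plan need a written rule for turning the paired pupil readings into one PRD, and a count of the tests that split at 0.10 mm?

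*Combined protocol and SAP*

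**What the plan says.** All of this is in the Study Protocol, Group 2, and the Statistical Analysis Plan.

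- Step 2, before the stimulus: "2 measurements will be made to establish a stable baseline".
- Step 4, after the stimulus: "2 measurements will be made, the first within 30 seconds of laryngeal stimulus, the second within 30 seconds of the 1st measurement". The next sentence is "PRD = Post-stimulus pupil size - pre-stimulus pupil size", one size minus one size.
- Step 5: "If PRD < or = 0.10 mm, extubate"; otherwise "If PRD > 0.10 mm, deepen patient with increments of propofol and/or fentanyl at anesthesiologist discretion, then repeat sequence of" measurement, stimulus and decision.
- Step 6: "If protocol iterates 3 times, the anesthesiologist will extubate when clinically appropriate irrespective of PRD".
- The SAP lists mean, median and standard deviation for age, sevoflurane concentration and pupillometry, and one t test between groups on Outcome #1. It plans no counts or proportions.

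The related aims are Aim 2, "Define an objective, quantitative metric to guide extubation in anesthetized pediatric patients", and Aim 4, "Compare pupillometry method to a traditional extubation method".

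**The concern.** Four readings go in and one number comes out, with no stated rule for reducing either pair. The post-stimulus readings are also taken at different moments: the second can be as late as 30 + 30 = 60 seconds after the stimulus. They may therefore differ because the response is changing, not only because of reading error.

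Step 5 has two branches and none for readings that disagree. Two anesthesiologists who both follow the text could look at identical numbers and act differently. One would extubate; the other would deepen and repeat. For such a test the text fixes neither the metric that Aim 2 sets out to define nor the Group 2 treatment that Aim 4 compares, and adherence to step 5 cannot be judged. The SAP has no tally that would show how often this arose, although the readings needed for one are already taken.

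**Working it through.** **Inputs.** From the documents: two readings before and two after each stimulus, the 0.10 mm line, and the limit of three iterations. The documents give no reading error, no distribution of PRD and no group size, so every frequency below rests on an assumption. There is no figure in the plan to reproduce.

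**When the post-stimulus summary matters.** Fix a baseline. Let L be the lower post-stimulus reading minus that baseline, and H the higher one minus it. The first, second, mean and larger readings all give a PRD between L and H. If H ≤ 0.10, all say extubate; if L > 0.10, all say repeat. They can differ only when L ≤ 0.10 < H.

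Example with baselines 2.00 and 2.00, then 2.14 and 2.04 mm:
- first or larger: 2.14 − 2.00 = 0.14, repeat
- second: 2.04 − 2.00 = 0.04, extubate
- mean: 2.09 − 2.00 = 0.09, extubate

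**The baseline pair has the same gap.** Take pre-stimulus 2.00 and 2.06, post-stimulus 2.14 and 2.15 mm:
- first baseline 2.00: PRD 0.14 and 0.15, repeat
- mean baseline 2.03: PRD 0.11 and 0.12, repeat
- second baseline 2.06: PRD 0.08 and 0.09, extubate

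Under each of these baselines the two post-stimulus readings agree, yet the step 5 result changes with the baseline. So the condition L ≤ 0.10 < H limits disagreement only once the baseline is fixed.

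**How often, simple model (assumed).** Let the two post-stimulus readings differ by g ≤ 0.10 mm and let L be spread evenly over 0 to W mm. Then P(0.10 − g < L ≤ 0.10) = g/W.

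| g (mm) | W = 0.5 | W = 1.0 |
|---|---|---|
| 0.02 | 4% | 2% |
| 0.05 | 10% | 5% |
| 0.10 | 20% | 10% |

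If no test falls near the line, the share is zero.

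**How often, error model (assumed).** Independent normal reading error, mean of the two baselines, 400,000 simulated tests per setting. Entries are the share of tests whose two PRDs fall on opposite sides of the line.

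| True PRD (mm) | SD 0.02 | SD 0.05 | SD 0.10 |
|---|---|---|---|
| 0 | 0.0% | 8.6% | 26.7% |
| 0.05 | 3.7% | 26.7% | 35.6% |
| 0.10 | 39.3% | 39.0% | 39.2% |
| 0.15 | 3.7% | 26.7% | 35.7% |
| 0.20 | 0.0% | 8.7% | 26.8% |
| 0.15 fading to 0.05 | 95.8% | 62.2% | 46.2% |

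The middle row has a closed form. The two PRDs share a baseline with variance σ²/2, so their correlation is (σ²/2)/(σ² + σ²/2) = 1/3, and P(opposite sides) = arccos(1/3)/π = 0.392. That row is the least favourable case for a constant response. In it, the share sent to extubation is about 50% with the first reading or the mean, 70% with the lower reading and 30% with the higher. The split there is reading noise at a threshold. A written rule would make the call repeatable but would not make it more informative.

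**What a planned count would show.** Exact 95% limits for assumed numbers of first tests:

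| First tests | None split: upper limit | 20% split: interval |
|---|---|---|
| 20 | 16.8% | 5.7–43.7% |
| 30 | 11.6% | 7.7–38.6% |
| 50 | 7.1% | 10.0–33.7% |
| 100 | 3.6% | 12.7–29.2% |

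For no events the upper limit is 1 − 0.025^(1/n). In a small group the count would be imprecise. It would also need a named baseline before two analysts could be sure of classifying a test alike.

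**Effect on the planned analyses.** The t test compares randomized groups on Outcome #1, which these documents do not define further. Step 5's repeat branch calls for propofol or fentanyl and sets no new vapor level. No route from the choice of summary to a changed t test can be shown from the text. The descriptive statistics for pupillometry can be computed under any summary.

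**The case for a change.** The strongest case for a change is that PRD is the metric of Aim 2 and the feature that distinguishes Group 2. A number used to decide extubation should be defined completely enough for another center to reproduce it. One sentence would do that with no new measurements. The mean may well have been intended, but the text does not say so, and step 6 does not resolve a split within a single test.

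Much of this stands. The text is incomplete for both pairs, and nothing elsewhere in the documents completes it. A published PRD without its definition would be hard to reuse.

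It does not establish a fault in the plan. The passages do not contradict one another, and no stated rule is shown to be wrong. Any ordinary summary fits the formula. Which reading should govern extubation is for the investigators, and none is proposed here. Whether operators actually differed is unknown. Group 2 already leaves the drug increments, and extubation after three iterations, to the anesthesiologist, so some variation between operators is part of the strategy being compared. Imposing one summary would also not be neutral at the bedside, since it would change action wherever practice does vary. A tally of split tests, or of extubations by step 5 versus step 6, is optional description that alters no planned result.

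**Conclusion.** The omission is real, but it does not call for a change. It is a gap in detail that users of the plan fill with any ordinary summary, applied consistently and named when PRD is reported. With a fixed baseline, the choice of post-stimulus summary matters only when L ≤ 0.10 < H; the choice of baseline summary can matter as well.

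The size in this trial cannot be known from the documents. The illustrations run from zero, through 2–20% under an even spread, to about 39% for a response exactly on the line and 46–96% for a response that fades across it. They rest on assumed gaps, spreads and reading errors, and the last two place the response at or across the threshold by construction. No effect on the Outcome #1 comparison is shown. The conclusion would be different if there were evidence that operators used different summaries and that this moved Outcome #1; the documents contain none.

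### The only planned comparison is an unadjusted t test of unstated variance form; a model with age, robust standard errors and a 95% CI would be a cheap improvement.

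*Combined protocol and SAP*

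**What the plan says.** The Statistical Analysis Plan section has two elements. The first is descriptive: "Calculation of descriptive statistics (mean, median, standard deviation) for parameters", followed by age, sevoflurane concentration and pupillometry. The second is the only between-group analysis: "Estimation of differences between Groups on Outcome #1 with comparison by T test". No covariate, variance form, confidence level or alpha is given, and Outcome #1 is not defined anywhere in the document.

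The Study Protocol section says that "subjects will be randomized to two groups". It gives no allocation ratio, blocking or sample size. Group 1 has a single vapor target, "anesthetic vapor set at 1.5 MAC (sevoflurane ~3.75%) for 8 minutes". Group 2 has an upper bound and clinician discretion: "anesthetic vapor set at < 0.5 MAC together with titrated increments of propofol and fentanyl as appropriate at discretion of anesthesiologist".

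**The concern.** Two features of the planned test deserve attention.

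- **Age is listed but not used.** The trial enrolls children, and age could be related to outcomes that depend on the child, such as airway events, time to extubation or an end-tidal concentration. If it is, an unadjusted test gives a wider interval than the data allow.
- **The form of the t test is open.** A pooled test assumes equal spread. For a vapor outcome, one arm has a single target and the other may lie anywhere below a ceiling, so equal spread is unlikely. Because the SAP's stated task is to estimate a difference, the interval is itself a result, and its coverage matters as well as the p-value.

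At stake are some precision and, in some configurations, the accuracy of the interval. Leaving both choices open also allows the pooled, Welch or adjusted result to be picked after the data are seen.

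**Working it through.** The plan states no sample size, SD, effect size, alpha or age-outcome correlation, so it has no figure to reproduce. Everything below is a scenario. Only the vapor settings come from the document.

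**1. Age adjustment.** Let r be the age-outcome correlation (assumed). Residual variance falls by r², interval width is multiplied by √(1 − r²), and the equivalent sample multiplier is 1/(1 − r²).

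| r | Variance reduction | Width ratio | Sample multiplier |
|---|---|---|---|
| 0 | 0% | 1.00 | 1.00 |
| 0.2 | 4% | √0.96 = 0.98 | 1.04 |
| 0.5 | 25% | √0.75 = 0.87 | 1.33 |
| 0.6 | 36% | √0.64 = 0.80 | 1.56 |

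**2. Cost when age is irrelevant.** With n per arm, the adjusted width is multiplied by about √(1 + 1/(2n − 4)), times the ratio of t quantiles after losing one degree of freedom. At n = 10 this is √(1 + 1/16) × 2.110/2.101 = 1.031 × 1.004 = 1.035, or about 3.5% wider. The same calculation gives 1.5% at 20 per arm and 0.5% at 50.

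**3. Spread if Outcome #1 is a vapor concentration.** The Group 1 setting implies 1 MAC ≈ 3.75/1.5 = 2.5% sevoflurane, so the Group 2 ceiling is 0.5 × 2.5 = 1.25%. If Group 2 values are uniform over 0 to 1.25% (assumed), their SD is 1.25/√12 = 0.36 points. Group 1 SD is assumed to be 0.05.

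**4. Coverage of a nominal 95% interval.** Simulated with normal data and the SDs above; total N of 50 is assumed.

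| Group 1 / Group 2 | Pooled | Welch |
|---|---|---|
| 25/25 | 94% | 95% |
| 30/20 | 88% | 95% |
| 33/17 | 83% | 95% |
| 20/30 | 98% | 95% |
| 17/33 | 99% | 95% |

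At equal arm sizes the pooled and Welch standard errors are identical and only the degrees of freedom differ. Even an SD ratio of 0.01 therefore lowers pooled coverage only to about 93.5% at 10 per arm and 94.3% at 20 per arm.

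**5. How likely is a damaging split?** Under simple randomization of 50, a 30/20 or worse split in either direction has probability 0.203. Undercoverage needs Group 1 to be the larger arm: P(Group 1 ≥ 30) = 0.101 and P(Group 1 ≥ 33) = 0.016. Averaged over all splits, pooled coverage is 93.8%, about one point below nominal.

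**6. Does it change the answer for a vapor outcome?** The settings differ by more than 3.75 − 1.25 = 2.5 points. At 33/17 with the assumed SDs:
- pooled SD = √[(32 × 0.05² + 16 × 0.36²)/48] = 0.212, so the half-width is 2.01 × 0.212 × √(1/33 + 1/17) ≈ 0.13;
- Welch half-width ≈ 2.12 × √(0.05²/33 + 0.36²/17) ≈ 0.19.

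The discrepancy is about 0.06 points on a gap of at least 2.5.

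**The case against.** The strongest reply has four parts.

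- **The two halves rest on different outcomes.** Unequal spread is argued from vapor settings, yet age should explain almost nothing of a dial setting. For outcomes where age might matter, the document gives no information on spread. This stands: the two harms should not be presented as occurring together. It does not remove the case for one specification that is sound under either reading.
- **A pooled test is not in the plan.** The term used covers Welch as well. This stands: the coverage figures describe what could happen if the pooled form were chosen.
- **The unadjusted comparison is unbiased.** Chance imbalance in age is ordinary sampling variation already reflected in the standard error. This stands in full.
- **For set sevoflurane, no conclusion could change.** The difference is imposed by design and dwarfs any interval error. This stands for the test result. It matters less for the reported interval, since estimation is the declared purpose.

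A reader might infer more: that the design rules out equal spread, that precision is certainly lost, or that the planned analysis is invalid. The document supports none of these. It gives no SD for either arm, no evidence that age predicts the outcome, and no definition of Outcome #1.

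**Conclusion.** The point holds as a low-cost improvement in efficiency and robustness. Three facts are established: there is one comparison, it is unadjusted and of unstated variance form, and age is only described.

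The size of the benefit is conditional. The precision gain depends on an age-outcome correlation that the document does not give, and may be zero. Misstated coverage requires three things together: a vapor-type outcome with unequal spread, a pooled test, and unequal arms. The low-spread arm must be the larger one for the interval to be too narrow. Under the assumed SDs and simple randomization of 50, the average loss is about one percentage point, though particular splits are considerably worse. Naming Outcome #1 comes first, because neither the model nor the covariate can be settled until that is done.

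**What to change.** Name Outcome #1, then replace the t-test sentence with one of the following.

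- **Continuous outcome:** The between-group difference in Outcome #1 will be estimated, by assigned group, from a linear model with terms for group and age, using heteroscedasticity-robust (HC3) standard errors, with a 95% confidence interval. An unadjusted Welch t test will be reported in support.
- **Yes/no outcome:** Outcome #1 will be analyzed, by assigned group, with a logistic model with terms for group and age, reported as a standardized risk difference with a 95% confidence interval.

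The cost is a short SAP edit and little extra programming, with no new data because age is already listed. For the linear model, the statistical price is one degree of freedom, which matters only if age is unrelated to the outcome and the arms are very small.
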